### *Power Calculation*

33

Version date 4/17/19

CCF #7

NCT02451176

We are investigating two primary outcomes: surgical site occurrences requiring procedural intervention (SSOPI) and hernia recurrence (HR). Surgical site occurrences requiring procedural intervention (SSOPI) is a repeated binary outcome measurement. Hernia recurrence (HR) is a single binary outcome measurement. In a multi-institutional retrospective review of clean-contaminated and contaminated ventral hernia repair, hernia recurrence rates were 29.21% versus 9.01%, and surgical site occurrences requiring procedural intervention were 39.02% versus 9.01% for the biological mesh and permanent synthetic mesh cohorts, respectively.[44] Based on review of these multi-institutional data, an estimated 253 patients will be enrolled in the proposed trial. Assuming a maximum 20% loss to follow-up, 202 patients will remain in the study sample for a 1:1 randomized allocation to each treatment arm (101 subjects per cohort). At the two-tailed overall (two hypotheses) type I error rate of 0.05, the study will have 92% power to detect a significant difference in the rates of hernia recurrence (29.21% vs. 9.01%), and a 100% power to detect a significant difference in surgical site occurrences requiring surgical intervention for the primary hypothesis (39.02% vs. 9.01%; with four repeated measurements and autoregressive correlation of  $\rho=0.5$ ) With 4 centers each performing approximately 1 eligible procedures per week, there will be 192 total procedures performed per year, from which it would be feasible to achieve the total enrollment goal of 253 subjects within 2 years.

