We hypothesize that reinforcement of single-stage open repairs of complex abdominal wall defects with a macroporous light-weight polypropylene synthetic mesh will result in significantly lower rates of hernia recurrence (HR) and surgical site occurrences requiring procedural intervention (SSOPI) at 24 postoperative months, and greater cost-effectiveness compared to reinforcement with a biologic mesh. We further hypothesize that reinforcement with macroporous light-weight polypropylene synthetic mesh will be associated with a significantly greater change in preoperative to postoperative patient-reported quality of life (QOL) compared to reinforcement with biologic mesh for clean-contaminated or contaminated ventral hernias.

The specific aims of the proposal are:

1. To demonstrate that a single-stage repair of clean-contaminated (Class 2) or contaminated (Class 3) ventral hernias using a macroporous light-weight polypropylene synthetic mesh will result in superior clinical outcomes compared to a biologic mesh.
  - a. Task 1- Demonstrate that repairs of clean-contaminated and contaminated ventral hernias performed with macroporous light-

weight polypropylene mesh will result in fewer recurrent hernias and fewer surgical site occurrences requiring procedural intervention at 24 postoperative months compared to repairs of clean-contaminated and contaminated ventral hernias performed with biologic mesh.

- b. Task 2- Compare postoperative pain, and demonstrate greater change in preoperative to postoperative quality of life (QOL) at 1 month, 6 months, 12 months, and 24 months following clean-contaminated or contaminated ventral hernia repair with a macroporous light-weight polypropylene mesh versus a biologic prosthesis.

2. To demonstrate that a macroporous light-weight polypropylene mesh is the more cost-effective strategy than a biologic prosthetic in clean-contaminated and contaminated abdominal wall reconstruction.

- a. Task 1-Estimate direct and indirect economic costs associated with clean-contaminated or contaminated ventral hernia repair using either polypropylene mesh or biologic mesh from a limited societal perspective.
- b. Task 2 – Perform health utility valuation in patients undergoing repair of clean-contaminated or contaminated ventral hernias using either polypropylene mesh or biologic mesh.
- c. Task 3 – Calculate and compare incremental cost-effectiveness ratios for patients undergoing repair of clean-contaminated or

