## STUDY DESIGN

We propose a multi-center prospective double-blinded randomized controlled trial comparing 253 patients with clean-contaminated (Class 2) or contaminated (Class 3) abdominal wall ventral hernias undergoing single-stage open repair. Soft Mesh™ by CR Bard™, a macroporous monofilament

polypropylene permanent mesh, will be compared to Strattice™ mesh by LifeCell™, a non-crosslinked porcine dermal biologic graft, for the single-stage open reconstruction of clean-contaminated and contaminated abdominal wall defects. The primary outcome variables will be the absence of surgical site occurrence requiring procedural intervention and the absence of a hernia recurrence from the time of surgery up to 24 months of postoperative follow-up.

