### **Study Procedures**

Patients undergoing open ventral hernia repair for clean-contaminated and contaminated abdominal wall hernias meeting inclusion criteria will be randomized to receive a synthetic mesh or a biologic mesh. Randomization will be carried out using computer-generated randomization blocks at the time of enrollment. Stratified randomization will be used with the strata formulated by medical center then by clean-contaminated or contaminated surgical site class. The Investigator will be blinded to patient randomization assignment until the point of intra-operative device use following final CDC wound classification, whereas patients and co-investigators responsible for data analysis will remain blinded to patient randomization until the conclusion of the study period. As such, a double-blinded study protocol will be maintained. Patients randomized to synthetic mesh will receive Soft Mesh™ (CR Bard™, Murray Hill, NJ), and those patients randomized to biologic mesh will receive Strattice™ (LifeCell™, Branchburg NJ). The use of biologic and synthetic meshes in clean-contaminated and contaminated fields is considered experimental; however, the

selection of these prosthetics was based on a careful review of the multiple animal models, preclinical data, and our own clinical experience with each of these materials placed in both clean and contaminated abdominal wall reconstructions.[26, 30-35]

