### **SUBJECT PRIVACY AND DATA CONFIDENTIALITY**

Anonymity and confidentiality of subjects participating in this study will be maintained. The only potential identifiers on any study documents submitted to the sponsor or designee will be subject study numbers, dates of birth, and dates of procedures. Every effort will be made to maintain the confidentiality of documents that identify the subject by name (e.g., signed informed consent documents, clinic charts), except to the extent necessary to allow monitoring by the Center for Clinical Research at Cleveland Clinic, internal monitoring by any of the participating sites, or auditing by the FDA or other regulatory authorities. Should the name and/or address of a subject participating in this trial be on a document submitted to the FDA or other regulatory authority (e.g., laboratory

report), the name and/or address will be completely blocked out and replaced with the subject study number.

Additionally, patient charts and clinical records will be requested and reviewed so that protocol adherence and source documentation can be verified. There is a possibility that the Institutional Review Boards of any of the participating sites, the Food and Drug Administration, and possibly foreign regulatory agencies may review the de-identified study records.

All information collected, such as name or medical record number, will be stored utilizing a customized Research Electronic Data Capture (REDCap®) database program for multi-institutional data collection. This is in a secure network/firewall protected electronic database to which only the investigator and the designated members of the study team will have access using an individual assigned login and password. Only approved study members listed on the IRB protocol will have access to the separately-stored master list. User rights will be assigned such that the designated research coordinator at each site may only enter and review data from that site. Only the Principal Investigator, Lead Research Coordinators, and Biostatisticians will be granted access to retrieve patient data from all sites for routine data quality assessments and data analyses. All electronic records pertaining to the clinical study will be password-protected, and only approved study members listed on the IRB protocol will have password access.

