### **Primary Analyses of Primary Outcomes:**

The primary outcomes are rates of surgical site occurrences requiring procedural intervention (SSOPI) and hernia recurrence (HR) assessed postoperatively at 1 month, 6 months, 12 months, and 24 months. For SSOPI with 4 repeated binary measurements, a generalized mixed model analysis with repeated measures will be performed to determine if a significant difference exists between the biologic mesh and the permanent synthetic mesh cohorts in the rate of SSOPI. For HR, which is a single binary outcome, simple chi-square tests will be used for unadjusted analyses and a logistic regression model will be used for adjusted analyses. As this is a randomized trial, differences in baseline demographic and clinical characteristics between the biologic mesh cohort and the permanent synthetic mesh cohort are expected to occur at random. Any significant differences found among the demographic or preoperative clinical characteristics between the two treatment groups will be controlled for in the final analysis to limit potential confounding of results.

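### Two primary outcomes share an overall 0.05, but the analysis section gives no testing rule and no deciding hernia recurrence test; Holm would keep the 0.05 and raise recurrence power from 92.8% to 96.0% if the wound outcome rejects as planned

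*Combined protocol and SAP*

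**What the plan says.** The Power Calculation section names SSOPI and hernia recurrence as the two primary outcomes. It fixes the error rate for the pair: "At the two-tailed overall (two hypotheses) type I error rate of 0.05, the study will have 92% power" for recurrence at 29.21% against 9.01%, and 100% power for SSOPI at 39.02% against 9.01%. No level per outcome is given.

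The section on primary analyses of primary outcomes says both outcomes are assessed at 1, 6, 12 and 24 months. SSOPI gets a repeated-measures mixed model. Recurrence is called a single binary outcome, for which "simple chi-square tests will be used for unadjusted analyses and a logistic regression model will be used for adjusted analyses". Neither recurrence test is ranked above the other. The section then adds: "Any significant differences found among the demographic or preoperative clinical characteristics between the two treatment groups will be controlled for in the final analysis". It states no significance level, no rule linking the two outcomes and no success criterion.

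Two other places bear on the reading. Study Design fixes the recurrence period: "the absence of a hernia recurrence from the time of surgery up to 24 months of postoperative follow-up". Specific Aims joins the outcomes with 'and': "significantly lower rates of hernia recurrence (HR) and surgical site occurrences requiring procedural intervention (SSOPI) at 24 postoperative months".

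**The concern.** An overall error rate for two hypotheses has to be carried into the analysis by a rule, and here it is not. Three matters are left open.

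- **The level for each outcome.** The 92% implies 0.025 each, but a reader of the analysis section alone could test each at 0.05 and claim either. That would break the overall 0.05.
- **The test that decides recurrence.** An unadjusted and an adjusted analysis are both listed, and the covariates in the final model depend on baseline significance tests.
- **What counts as success.** The wording of the hypothesis could mean that both outcomes are required. The phrase about two hypotheses, and the 92%, point instead to a split.

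Even if the implied split is intended, it is not the best use of the error rate. Recurrence is the weaker-powered outcome and bears the cost of a fixed 0.025, while SSOPI has power to spare.

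**Working it through.** **Inputs (Power Calculation).** Overall two-sided 0.05 over two hypotheses; 253 enrolled, 20% loss, 101 per arm; recurrence 29.21% vs 9.01%; SSOPI 39.02% vs 9.01% with four measurements and autoregressive correlation 0.5. Sample size check: 202 / 0.8 = 252.5, rounded up to 253, as stated.

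**1. Reproduce the 92%.** Pooled z test, power = Φ[(d − z·SE0) / SE1].
- d = 0.2921 − 0.0901 = 0.2020; mean rate 0.1911.
- SE0 = √(2 × 0.1911 × 0.8089 / 101) = 0.05533.
- SE1 = √(0.2921 × 0.7079 / 101 + 0.0901 × 0.9099 / 101) = 0.05347.
- At 0.025 (z = 2.2414): Φ(1.459) = **92.8%**.
- At 0.05 (z = 1.9600): Φ(1.750) = **96.0%**.

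Exact enumeration of the chi-square test gives 93.8% and 96.7%. The stated 92% therefore fits 0.025 per outcome.

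**2. Recurrence power under Holm.** The smaller p-value is tested at 0.025 and, if significant, the other at 0.05. Recurrence is thus tested at 0.05 whenever SSOPI is significant at 0.025. If P is the SSOPI power at 0.025 and the outcomes are independent (assumed), recurrence power = 0.960·P + 0.928·(1 − P).

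For P, take the mean of four visits. With AR(1) 0.5 the variance factor is 0.516. The rates are read as per-visit rates; all pairs after the first are assumed.

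| SSOPI rates | P | Recurrence power, Holm |
|---|---|---|
| 39.02% vs 9.01% (plan) | >0.999 | 96.0% |
| 35% vs 15% | 0.992 | 96.0% |
| 30% vs 15% | 0.909 | 95.7% |
| 25% vs 15% | 0.593 | 94.7% |
| equal | 0.025 | 92.8% |

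**3. Smaller recurrence effect.** If the biologic rate were 25% (assumed) against 9.01%, the pooled z power is 78.9% at 0.025 and 86.2% at 0.05, the latter applying under Holm if SSOPI rejects.

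**4. Error if the overall level is not carried over.** With each outcome at 0.05 and a claim for either: 1 − 0.95² = 9.75% if independent. Simulation with a correlation of 0.5 between the test statistics (2,000,000 draws) gives 9.1%.

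**5. How often the adjustment rule would change the model.** With 8 to 12 independent baseline characteristics (assumed), the chance that at least one reaches p < 0.05 is 1 − 0.95⁸ = 33.7% to 1 − 0.95¹² = 46.0%. This is how often the rule is triggered, not an error rate.

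**6. A stratified recurrence test costs almost nothing.** With eight near-equal strata carrying no risk (assumed; 100,000 simulations), Mantel-Haenszel power is 93.65% and 96.58% at the two levels, against 93.76% and 96.71% unstratified.

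**7. If both outcomes are required.** Each is tested at 0.05, and joint power at the planned rates is 96.0%.

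**The case against.** The strongest reply is that little is broken. The overall 0.05 is stated in the same document, so reaching 9.75% means ignoring it. A fixed 0.025 split is valid, and writing 0.025 down would close the gap. Holm then adds 3.2 points to an outcome already above 90%, and only if SSOPI rejects. That is not assured, since the protocol itself expects that synthetic mesh may bring more early mesh infections. These points are fair on weight. They do not supply the missing rule, and Holm cannot do worse than the split.

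The recurrence time point is also clearer than the analysis section suggests, because Study Design fixes it at up to 24 months. That stands, and the fix uses it.

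The secondary time-to-event section calls the unadjusted analysis sufficient and treats post-hoc covariate selection as inferior. That shows the sponsor's thinking and supports making such adjustment supportive, but it does not govern the primary analyses, where the text says the opposite.

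A null simulation of the baseline-driven rule (101 per arm, about 19% recurrence, 8 or 12 independent normal covariates, 20,000 runs per setting) gave error of 0.020 to 0.024 at nominal 0.025 and 0.044 to 0.050 at 0.05. Choosing the better of the two p-values gave 0.025 to 0.027 and 0.054 to 0.057. No material inflation is therefore claimed; the problem is that the deciding model is not fixed in advance.

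Finally, the document refers to patients already enrolled, and Holm relaxes the implied recurrence threshold mid-trial. This is a real constraint on timing and documentation, and the fix has to meet it.

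**Conclusion.** The concern holds. The plan commits to an overall 0.05 over two outcomes, and its 92% implies 0.025 each. The analysis section gives no rule to deliver this, and it lets the final recurrence model depend on the baseline data. The sample size and the 92% are correct.

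Holm keeps the overall 0.05 whatever the dependence between outcomes. Its gain in recurrence power is 3.2 points (92.8% to 96.0%) at the planned rates if SSOPI rejects, 7.3 points (78.9% to 86.2%) if the biologic recurrence rate is 25%, and nothing if SSOPI does not reject. These figures assume 101 evaluable per arm and an unadjusted recurrence test. The intermediate values also assume independent outcomes and per-visit SSOPI rates that the plan does not give. This should be corrected, but it does not threaten the design.

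**What to change.** Make a dated amendment before the analysis team is unblinded, recording that no comparison by arm had been made.

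In the primary analysis section:
1. Test the SSOPI mixed-model overall treatment effect across the four visits, and one named recurrence test covering surgery to 24 months, by Holm: the smaller p-value at 0.025 and, if significant, the other at 0.05. Make a separate claim for each outcome.
2. Name the deciding recurrence test, for example the unadjusted chi-square already listed. A chi-square stratified by centre and wound class, the randomization strata, would serve equally if named now.
3. Amend the sentence on baseline differences so that adjustment for observed imbalance is supportive and decides neither primary result.

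In the Power Calculation section, write the 0.025 explicitly, keep 92% as the recurrence power at that level, and add about 96% under Holm if SSOPI rejects. If both outcomes must be significant, say so instead; each is then tested at 0.05 and Holm is not needed. If the record of no comparison cannot be made, the fixed 0.025 split remains valid and should be written down.

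The cost is text edits in two sections, with no change to enrolment, sample size or data collection. The record matters. Study Procedures says "patients and co-investigators responsible for data analysis will remain blinded to patient randomization until the conclusion of the study period", but the surgeon learns the allocation in theatre. The confidentiality section adds: "Only the Principal Investigator, Lead Research Coordinators, and Biostatisticians will be granted access to retrieve patient data from all sites". One small drawback is that confidence intervals matching Holm are less simple; 97.5% intervals can still be reported.

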### *Analysis*

**Specific Aim 1** - To demonstrate that a single-stage repair of clean-contaminated (Class 2) or contaminated (Class 3) ventral hernias using a

macroporous light-weight polypropylene synthetic mesh will result in superior clinical outcomes compared to a biologic mesh.

### **Primary Analyses of Primary Outcomes:**

The primary outcomes are rates of surgical site occurrences requiring procedural intervention (SSOPI) and hernia recurrence (HR) assessed postoperatively at 1 month, 6 months, 12 months, and 24 months. For SSOPI with 4 repeated binary measurements, a generalized mixed model analysis with repeated measures will be performed to determine if a significant difference exists between the biologic mesh and the permanent synthetic mesh cohorts in the rate of SSOPI. For HR, which is a single binary outcome, simple chi-square tests will be used for unadjusted analyses and a logistic regression model will be used for adjusted analyses. As this is a randomized trial, differences in baseline demographic and clinical characteristics between the biologic mesh cohort and the permanent synthetic mesh cohort are expected to occur at random. Any significant differences found among the demographic or preoperative clinical characteristics between the two treatment groups will be controlled for in the final analysis to limit potential confounding of results.

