The abdominal wall is reconstructed by initially incising the posterior rectus sheath just lateral to the linea alba. The release is performed at least 5 centimeters above and below the fascial defect. The posterior rectus sheath is then separated off the rectus muscle to the linea semilunaris. If additional release is necessary to achieve fascial closure, the transversus abdominis muscle or the external oblique muscle may be released at the discretion of the surgeon and documented. The posterior components are then reapproximated to exclude the abdominal viscera from the mesh. If the mesh cannot be placed in the retro-rectus or preperitoneal position, then the patient will be excluded from the study. Unless contraindicated due to drug allergies, a pulse lavage antibiotic irrigation using a 3 liter bag with Gentamycin (240 mg), Ancef (3gm), and Bacitracin (50,000 units) will be applied to the posterior rectus sheath and subcutaneous tissues after the components are reapproximated and prior to mesh placement. If there is a drug allergy, then pulse lavage irrigation with sterile saline only will be applied. Final wound classification will occur just prior to mesh placement per CDC criteria. Surgical wounds will be classified based on CDC criteria and only Class 2 and 3 wounds will be included in this study (see Appendix 3):

20

Version date 4/17/19

CCF #7

NCT02451176

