## Class 3- Contaminated

A surgical field with any of the following: open, fresh, accidental wounds; operations with major breaks in sterile technique or gross spillage from the gastrointestinal tract; and incisions in which acute, nonpurulent inflammation is encountered.

Following wound classification, the allocation of the patient to either the biologic mesh cohort or the permanent synthetic mesh cohort will be revealed to the operating surgeon, according to the previously-described computer-generated block randomization scheme stratified by wound classification and medical center. The corresponding prosthetic material will then be placed with at least 5

cm of fascial coverage on all sides of the defect. The mesh will be fixated with trans-abdominal #1 Maxon or PDS sutures at 5-10 cm intervals. Number of sutures to secure the mesh will be documented. All patients will have closed suction drains placed above the mesh and below the fascial closure. These drains will be removed postoperatively when the collected fluid is < 30 cc/day for 48 hours and documented. The fascia will be closed with a running or interrupted Maxon or PDS #1 suture. The skin will be closed loosely with staples. Dry sterile dressings will be placed at the conclusion of the procedure and will be removed on postoperative day 2. No further dressings will be applied to the wound.

Postoperative complications will be defined and recorded on the CRF's based on CDC standardized terms and definitions for Surgical Site Infections as follow: [42, 43]-See appendix 4.

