### **Secondary Analyses of Primary Outcomes:**

These primary outcomes will also be assessed as time-to-event analyses (time-to-a-healed-wound and time-to-hernia-recurrence, respectively). In these analyses, the time-to-recurrence in the synthetic mesh group will be compared to

the time-to-recurrence in the biologic mesh group using a two-sided log-rank test. The null hypothesis is that the time-to-recurrence is the same between the two groups ( $H_0$ : Hazard Ratio = 1), and the alternative hypothesis is that the time-to-recurrence is significantly greater for the permanent synthetic mesh cohort compared to the biologic mesh cohort ( $H_1$ : Hazard Ratio  $\neq$  1). Since this is a randomized clinical trial, observed differences in other covariates between the two study groups are assumed to arise by chance. Therefore, the simple unadjusted analysis is sufficient to answer the research question, assuming adequate power (see above). However, since the association between other covariates and time-to-recurrence may be of interest and because group imbalances may occur due to chance, it is of interest to consider further analyses that adjust for covariates in the relationship of time-to-recurrence and mesh type. To that end, the following multivariable models are pre-specified: 1) Demographics: age, race, gender, and mesh type; and 2) Known linkages to hernia recurrence: BMI, history of smoking, size of defect, number of previous hernia repairs, and mesh type. These models will be fit with Cox proportional hazards models. If other covariates are found to be highly imbalanced between groups or found to be associated with time-to-recurrence, they can also be included in multivariable models; however, this type of post-hoc model selection is to be considered inferior to the pre-specified models and is speculative in nature. A similar analysis will ensue for the time-to-a-healed-wound outcome. The null hypothesis is that the time-to-a-healed-wound is the same between the two groups ( $H_0$ : Hazard Ratio = 1), and the alternative hypothesis is that the

time-to-a-healed-wound is significantly greater for the permanent synthetic mesh cohort compared to the biologic mesh cohort (H1: Hazard Ratio not= 1).

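### The primary analysis adjusts for whatever differs at baseline, has no stated place for the wound-class stratum, and does not name the deciding hernia-recurrence test

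*Combined protocol and SAP*

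**What the plan says.** *Primary Analyses of Primary Outcomes* assigns a generalized mixed model with repeated measures to SSOPI. For HR, "simple chi-square tests will be used for unadjusted analyses and a logistic regression model will be used for adjusted analyses". It remarks that baseline differences in a randomised trial arise by chance, and then says: "Any significant differences found among the demographic or preoperative clinical characteristics between the two treatment groups will be controlled for in the final analysis". No test level, covariate list or deciding test is given.

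*Study Procedures* states: "Stratified randomization will be used with the strata formulated by medical center then by clean-contaminated or contaminated surgical site class". The text after the Class 3 wound definition repeats this as a "computer-generated block randomization scheme stratified by wound classification and medical center". *Study Procedures* places randomisation at enrollment but also says: "Final wound classification will occur just prior to mesh placement per CDC criteria".

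*Secondary Analyses of Primary Outcomes* says of time to recurrence that "the simple unadjusted analysis is sufficient to answer the research question, assuming adequate power (see above". It pre-specifies two Cox models: one with age, race and gender, the other with BMI, smoking, defect size and previous repairs. It ranks models chosen afterwards, from imbalance or association with outcome, below those two and treats them as speculative. Neither Cox model contains center or wound class.

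The last paragraph of *Analyses of Secondary Outcomes* plans to explore center effects and center-by-treatment interaction, with center indicators in the regression analyses.

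**The concern.** Three gaps meet in the primary analysis.

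- **Covariate rule.** Under randomisation, a significant baseline difference is a chance event and says nothing about whether the variable predicts outcome. The four factors that the plan itself links to recurrence enter the primary analysis only if they happen to be imbalanced. The plan calls this kind of selection inferior even for its secondary models.
- **Strata.** The factors used to balance the arms are not named in the primary models. The covariate rule will seldom bring wound class in, because stratification balances it by design.
- **Deciding test.** The reference to a final analysis points to the adjusted model. The remark that the unadjusted analysis is sufficient points to the chi-square, but it was written for the log-rank comparison.

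At stake is whether two competent analysts following the plan would report the same primary p-value for HR, and whether the stratification is used.

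**Working it through.** **1. The plan's own figure.** Inputs from *Power Calculation*: 29.21% vs 9.01%, 101 per arm, overall two-sided error 0.05 over two hypotheses. An equal split to 0.025 each is an inference.

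Mean rate = (0.2921 + 0.0901)/2 = 0.1911; difference = 0.2020.
Null SE = √(2 × 0.1911 × 0.8089/101) = 0.0553.
Alternative SE = √((0.2921 × 0.7079 + 0.0901 × 0.9099)/101) = 0.0535.
Power = Φ((0.2020 − 2.2414 × 0.0553)/0.0535) = Φ(1.46) = 92.8%.

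At 0.05 the result would be 96.0%, so the stated 92% fits an unadjusted two-proportion test at 0.025. Exact enumeration of the chi-square gives 93.8%. The sample size also reproduces: 202/0.8 = 252.5, rounded up to 253.

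**2. How often chance triggers adjustment.** *Study Procedures* lists 12 preoperative items. Nine remain if wound class, one of length and width, and medical history are not counted. For k independent tests at level a, P(at least one significant) = 1 − (1 − a)^k. The plan gives no level, so a is assumed.

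| a | k = 4 (the factors linked to recurrence) | k = 9 | k = 12 |
|---|---|---|---|
| 0.01 | 4% | 9% | 11% |
| 0.05 | 18% | 37% | 46% |
| 0.10 | 34% | 61% | 72% |

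These are trigger rates, not error rates or bounds. Correlation lowers them; counting laboratory values or splitting medical history raises them.

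**3. Whether the rule picks up wound class.** Simulation with 253 patients, 4 centers and 50% class 3 (assumed): with permuted blocks of 4, 6 or 8, the stratification class was never significant at 0.05. If 10, 20 or 30% of patients change class independently of arm (assumed, blocks of 4), the final class is selected in 0.2, 1.5 or 3.3% of trials.

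**4. Type I error.** Simulation with 8,000 trials per scenario, null rate 19.11%, 12 independent covariates of which 4 have log-odds 0, 0.4 or 0.6 per SD, and selection at 0.01, 0.05 or 0.10. If nothing is selected, the chi-square stands; otherwise a Wald logistic test is used. The rule rejects in 1.8-2.6% of trials and the chi-square in 2.3-2.6%. Claiming success if either is significant gives 2.4-2.9%. Monte Carlo SE is about 0.17 points.

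**5. Disagreement between the two HR tests.** Same simulation, selection at 0.05: 0.9-1.5% of trials at 29.21% vs 9.01%, and 3.2-5.2% at an assumed 25% vs 12%. A logistic Wald test with no covariates already disagrees with the chi-square in 0.7% and 2.0% of trials. With 12 tests, adjustment is triggered in about 46% of trials, so roughly 0.46 × 0.7 = 0.3 points and 0.46 × 2.0 = 0.9 points come from the choice of statistic and not from covariate selection.

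**6. Leaving out the strata.** With stratum risks p_k, the chi-square uses the variance p̄(1 − p̄). Stratified allocation removes the between-stratum part, leaving p̄(1 − p̄) − Var(p_k), so the test is conservative when p_k varies. Simulation: 400,000 trials, 8 strata, 101 per arm, level 0.025; stratum spreads assumed.

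| Spread of stratum risk | Power, chi-square → CMH | Size, chi-square → CMH |
|---|---|---|
| None | 93.8 → 93.7% | 2.50 → 2.47% |
| Moderate, 9-33% | 94.1 → 94.4% | 2.24 → 2.45% |
| Strong, 4-46% | 94.7 → 95.8% | 1.83 → 2.47% |

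A repeat under moderate and strong assumed spread gave gains of about 0.4 and 1.2 points and chi-square sizes of about 1.7-2.2%. The combined ranges are a gain of 0.3-1.2 points and a size of 1.7-2.2%. If only wound class matters, with odds ratio (0.15/0.85)/(0.08/0.92) = 2.03 borrowed from the infection rates in *Significance* and applied to recurrence by assumption, the gain is about 0.1 points.

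**7. SSOPI.** Simplified to any event per patient, power at 39.02% vs 9.01% is about 99.9% with or without strata. The repeated-measures model was not recomputed.

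**The case against.** Most of the case on the other side concerns weight, and much of it stands.

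- **The HR text can be read as one conditional rule:** chi-square if nothing is imbalanced, logistic regression if something is. That reading is available, so the plan is not incoherent. It still needs a test level and a candidate list, and the plan does not say that this is the rule that decides.
- **Center may already be covered.** The center paragraph promises indicator variables in the regression analyses and closes Aim 1, so it may reach the HR logistic model and the SSOPI mixed model. A reader might infer that center is missing altogether; the text does not support that. The omission is certain only for wound class.
- **An unstratified chi-square after stratified randomisation is valid.** This stands: the cost is conservatism and a little power.
- **The larger figures are assumed.** The 25% vs 12% rates, the stratum spreads and the covariate strengths are not in the documents.

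A reader might also infer that the rule lets the team choose covariates to suit the result. The documents do not support that. The rule looks only at baseline data, and "co-investigators responsible for data analysis will remain blinded to patient randomization until the conclusion of the study period". Even reporting whichever HR test succeeds would add only 0.1-0.3 points to the chi-square's error rate in step 4.

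**Conclusion.** The point holds as a weakness of pre-specification, at low severity. The covariate rule selects on chance, wound class is in no stated model, the reach of the center paragraph is unclear, and the deciding HR test is not named.

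The rule does not inflate type I error, and neither N = 253 nor the stated 92% changes. It would be wrong to read the omission of the strata as invalidating the test or undermining the power figure. What is lost is about 0.3-1.2 points of HR power at the design rates, and only if the strata carry the assumed moderate to strong spread; with no spread, nothing is lost. The two HR tests would disagree in about 1% of trials at the design rates with an assumed 0.05 selection level, and part of that is Wald versus chi-square. The reading of the text is secure. The sizes rest on assumed spreads, covariate strengths and an equal split of the error rate.

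**What to change.** Change the SAP wording as follows.

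1. Delete the baseline-significance rule, or keep it only as a labelled sensitivity analysis.
2. For HR, name the Cochran-Mantel-Haenszel test stratified by center and wound class as the deciding test, with the unadjusted chi-square and a logistic model as sensitivity analyses.
3. For SSOPI, name the mixed model with center and wound class as fixed effects.
4. State that the wound class in these analyses is the one used for stratification, after reconciling randomisation at enrollment with classification just before mesh placement.
5. State whether the center paragraph covers the primary outcomes.

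No new data are needed. If the strata are not prognostic, the Cochran-Mantel-Haenszel test costs about 0.1 points of HR power at the design rates and 0.2-0.3 points at an assumed 25% vs 12%. A Wald logistic test as the deciding analysis would cost somewhat more, about 0.3 and 0.7 points. The SSOPI cost was not computed for the repeated-measures model; in the any-event simplification there is none.
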